15.2 Randomization/Stratification

N/A.

15.3 Sample Size

The study is expected to include 2 dose groups. Up to 20 eligible participants will be accrued into each dose group to initiate agent intervention. We anticipate accruing 1 participant every two months until all sites are activated. Once all sites are activated, we anticipate accruing 1-2 participants every month, we expect to complete the accrual of each dose cohort in 20 months.

15.4 Primary Objective, Endpoint(s), Analysis Plan

The primary objective of this study is to determine the effects of low dose apalutamide on circulating levels of PSA. Percent changes in circulating levels of PSA from baseline will be measured. If the prostate biopsy was performed within 6 weeks prior to the baseline visit, the most recent prior PSA

instead of the PSA at the baseline visit will be used for the baseline value. The study is expected to have 2 dose groups. The dose level of the second dose cohort may be higher (escalation) or lower (de-escalation) than the first dose group, depending upon the PSA response in the initial cohort. Therefore, for the primary endpoint analysis we conservatively use Bonferroni correction while constructing the credible intervals for two dose groups. Specifically, the proportion of participant with $\geq 25\%$ decline in PSA levels (from baseline to end-of-intervention) for each dose cohort will be reported along with the 97.5% credible interval (CI) for the response rate based on the posterior distribution of the response rate derived from a non-informative prior for the response rate, which is consistent with the Bayesian approach used for dose escalation/de-escalation. A sample size of 20 participants produces a two-sided 97.5% CI for the response rate with a width no wider than 0.404 (based on an observed response rate of 50%).

Observed response rate	Width of 97.5% CI
5% (i.e. 1 responders)	0.226
10% (i.e. 2 responders)	0.273
15% (i.e. 3 responders)	0.309
20% (i.e. 4 responders)	0.337
25% (i.e. 5 responders)	0.359
30% (i.e. 6 responders)	0.376
35% (i.e. 7 responders)	0.389
40% (i.e. 8 responders)	0.397
45% (i.e. 9 responders)	0.403
50% (i.e. 10 responders)	0.404
55% (i.e. 11 responders)	0.403

In addition, the two-sided 97.5% credible interval (CI) for the mean percentage change in PSA for each dose group will be also constructed based on the posterior distribution of mean percentage change, in which the percentage change is assumed to follow a normal distribution and the prior distribution of the mean percentage change is also assumed to follow a normal distribution.

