16	NA	NA	NA	NA	100.00	99.99	99.96	99.87	99.64
17	NA	NA	NA	NA	NA	100.00	100.00	99.98	99.93
18	NA	NA	NA	NA	NA	NA	100.00	100.00	99.99
19	NA	100.00	100.00						
20	NA	100.00							

For the 60 mg MWF/wk dose, if the posterior probability is found to be $\geq 80\%$ at the evaluation (with the first evaluation starting after 12 evaluable participants), this dose cohort will be closed for efficacy and be de-escalated to 60 mg once a week schedule. If the posterior probability is found to be $\leq 20\%$ at the evaluation (with the first evaluation starting after 12 evaluable participants), this dose cohort will be closed for futility and be escalated to 60 mg daily dose. If the posterior probability is found to be $>20\%$

and <80%, the evaluation will be repeated with one additional evaluable participant, using the same criteria, up to a total of 20 evaluable participants.

If the regimen is escalated to 60 mg daily dose, the same probability criteria will be used to stop the dose cohort for efficacy or futility.

For the 60 mg once a week schedule, a PSA response rate of $\geq 25\%$ is considered sufficient for using this regimen as the starting regimen in future active surveillance studies.

The posterior probabilities of observing a response rate $\geq 25\%$ are summarized below based on the observed number of responders and a non-informative prior for 12-20 evaluable participants.

N_r	N=12	N=13	N=14	N=15	N=16	N=17	N=18	N=19	N=20
0	2.38	1.78	1.34	1.00	0.75	0.56	0.42	0.32	0.24
1	12.67	10.10	8.02	6.35	5.01	3.95	3.10	2.43	1.90
2	33.26	28.11	23.61	19.71	16.37	13.53	11.13	9.13	7.45
3	58.43	52.13	46.13	40.50	35.30	30.57	26.31	22.52	19.17
4	79.40	74.15	68.65	63.02	57.39	51.87	46.54	41.48	36.74
5	91.98	88.83	85.16	81.03	76.53	71.75	66.78	61.72	56.66
6	97.57	96.17	94.34	92.04	89.29	86.10	82.51	78.58	74.36
7	99.44	98.97	98.27	97.29	95.98	94.31	92.25	89.82	87.01
8	99.90	99.78	99.58	99.25	98.76	98.07	97.13	95.91	94.39
9	99.99	99.97	99.92	99.84	99.69	99.46	99.11	98.61	97.94
10	100.00	100.00	99.99	99.97	99.94	99.88	99.77	99.61	99.36
11	100.00	100.00	100.00	100.00	99.99	99.98	99.95	99.91	99.83
12	100.00	100.00	100.00	100.00	100.00	100.00	99.99	99.98	99.96
13	NA	100.00	100.00	100.00	100.00	100.00	100.00	100.00	99.99
14	NA	NA	100.00	100.00	100.00	100.00	100.00	100.00	100.00
15	NA	NA	NA	100.00	100.00	100.00	100.00	100.00	100.00
16	NA	NA	NA	NA	100.00	100.00	100.00	100.00	100.00
17	NA	NA	NA	NA	NA	100.00	100.00	100.00	100.00
18	NA	NA	NA	NA	NA	NA	100.00	100.00	100.00

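### The widths in Section 15.4 labelled 97.5% are uncorrected 95% credible-interval widths; at N=20 the true 97.5% maximum is 0.456, not 0.404

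*Combined protocol and SAP*

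**What the plan says.** Section 15.4 (Primary Objective, Endpoint(s), Analysis Plan) starts from this expectation: "The study is expected to have 2 dose groups". For that reason it says "for the primary endpoint analysis we conservatively use Bonferroni correction while constructing the credible intervals for two dose groups". Each cohort's proportion of participants with a PSA decline of at least 25% is to be reported with a 97.5% credible interval from a posterior "derived from a non-informative prior for the response rate, which is consistent with the Bayesian approach used for dose escalation/de-escalation".

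On precision, the section states "A sample size of 20 participants produces a two-sided 97.5% CI for the response rate with a width no wider than 0.404", with the maximum at an observed response rate of 50%. A table headed "Width of 97.5% CI" lists widths for 1 to 11 responders out of 20, from 0.226 at 1 responder to 0.404 at 10.

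Section 15.3 (Sample Size) gives the cohort size, "Up to 20 eligible participants will be accrued into each dose group to initiate agent intervention", without a power statement or a target width.

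**The concern.** A two-sided 97.5% interval leaves 1.25% in each tail; a 95% interval leaves 2.5%. The printed widths look too narrow for the level claimed. If they are 95% widths, the correction was announced in the text but not carried into the table.

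The sentence and table in Section 15.4 are the only interval precision the plan gives for the primary response rate at N=20. A reader judging whether 20 per cohort is informative enough would rely on them. The correction is also the reason the level is 97.5% at all. Two intervals at 97.5% guarantee joint coverage of at least 1 − 2 × 0.025 = 95% by Bonferroni; two intervals as narrow as those printed would guarantee only 1 − 2 × 0.05 = 90%.

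**Working it through.** **Inputs**
- N = 20 per cohort, and x = 1 to 11 responders (Section 15.4 table).
- Level 97.5%, two-sided: 0.05/2 = 0.025 outside the interval for each of two groups (Section 15.4).
- Prior: called non-informative, parameters not given, but tied by Section 15.4 to the monitoring rule in Section 15.1.

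**Step 1. Identify the prior.** Under a uniform Beta(1,1) prior the posterior is Beta(1+x, 1+N−x). It reproduces the Section 15.1 tables:
- 50% threshold, 4 of 12: 13.34% (printed 13.34). A Jeffreys prior gives 12.37 and the Haldane limit 11.33.
- 50% threshold, 12 of 20: 80.83% (printed 80.83).
- 25% threshold, 0 of 12: 2.38% (printed 2.38).

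The prior in use is therefore uniform.

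**Step 2. Compute equal-tailed widths at N=20.** With posterior Beta(1+x, 21−x):
- 95% width = quantile(0.975) − quantile(0.025)
- 97.5% width = quantile(0.9875) − quantile(0.0125)

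| Responders of 20 | Printed as 97.5% | Computed 95% | Computed 97.5% |
|---|---|---|---|
| 1 | 0.226 | 0.226 | 0.260 |
| 2 | 0.273 | 0.273 | 0.311 |
| 3 | 0.309 | 0.309 | 0.350 |
| 4 | 0.337 | 0.337 | 0.381 |
| 5 | 0.359 | 0.359 | 0.406 |
| 6 | 0.376 | 0.376 | 0.425 |
| 7 | 0.389 | 0.389 | 0.439 |
| 8 | 0.397 | 0.397 | 0.449 |
| 9 | 0.403 | 0.403 | 0.454 |
| 10 | 0.404 | 0.404 | 0.456 |
| 11 | 0.403 | 0.403 | 0.454 |

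All 11 printed values agree with the 95% column and none with the 97.5% column.

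**Step 3. Check the extreme row directly.** At 10 of 20 the 0.404-wide interval is 0.298 to 0.702 and holds 95.0% of the Beta(11,11) posterior. The 97.5% interval is 0.272 to 0.728, width 0.456.

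**Step 4. Try other constructions at 97.5%, 10 of 20.** Uniform highest-density 0.456; Jeffreys 0.466; Haldane 0.476; Wilson and Agresti-Coull 0.448; Wald 0.501; Clopper-Pearson 0.507. None gives 0.404. At 1 of 20 the uniform highest-density and Jeffreys equal-tailed 97.5% widths are both 0.237, not the printed 0.226.

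**Step 5. Size of the understatement.**
- At 1 of 20: 0.260 − 0.226 = 0.034, and 0.034/0.226 = 15%.
- At 10 of 20: 0.456 − 0.404 = 0.052, and 0.052/0.404 = 13%.
- By symmetry around 10, the 97.5% width exceeds 0.404 for 5 to 15 responders, which is 11 of the 21 possible outcomes.

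**Step 6. Outcomes that can occur at N=20.** Under Section 15.1, when the posterior probability lies between the stopping limits, "the evaluation will be repeated with one additional evaluable participant, using the same criteria, up to a total of 20 evaluable participants". If the rule is checked after each evaluable participant from 12 onward and the cohort stops as soon as a limit is met, enumerating the paths gives:
- 50% rule (three-times-weekly or daily cohort): N=20 is reached only with 8 to 12 responders. The 97.5% widths are 0.449 to 0.456, all above 0.404. The 95% widths are 0.397 to 0.404, none above it.
- 25% rule (once-weekly cohort): N=20 is reached only with 3 to 7 responders. The 97.5% widths are 0.350 to 0.439, and those for 5, 6 and 7 responders exceed 0.404.

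**The case against.** The strongest reply is that nothing operational depends on 0.404. Section 15.4 has the final intervals computed from the posterior at 97.5%, not read from this table, so the correction survives in the specified analysis. Dose decisions use the Section 15.1 probability tables, which reproduce. No target width was set that 20 participants now fail to meet. All of this stands: the 90% joint figure describes intervals of the printed width, not the intervals the plan says it will report. It limits the consequence to a misstated precision claim but does not make the claim right.

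Second, the plan never says the interval is equal-tailed. With highest-density intervals and the same prior, the 97.5% width at 5 of 20 is 0.401, so 9 rather than 11 outcomes (6 to 14) exceed 0.404, only 6 and 7 responders do so in the once-weekly case, and the excess at 1 of 20 is about 5% (0.237 against 0.226) rather than 15%. That is a fair qualification of the counts and the upper percentage. The maximum is 0.456 either way, and the printed table is itself equal-tailed: the highest-density 95% width at 1 of 20 is 0.205, not 0.226.

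Third, the responder counts in Step 6 assume that a cohort closes as soon as a limit is met. Participants already on drug at that point could still contribute data, so other counts at N=20 are possible. This is also fair, but the mislabelling does not depend on Step 6.

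**Conclusion.** The concern holds. The Section 15.4 sentence and all 11 table entries give 95% widths under a 97.5% label. The maximum 97.5% width at N=20 is 0.456, so the stated bound is too small by 0.052, and the true widths are 13 to 15% larger than printed.

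The percentages and the count of 11 outcomes assume a uniform prior and equal-tailed intervals, both inferred from the plan's own tables. The conclusion that 0.404 is wrong does not rest on them: every 97.5% construction tried gives at least 0.448 at 10 of 20. This should be fixed because it is the only interval precision stated for the primary response rate. It does not affect the dose-decision rule, the sample size or the choice of a 97.5% interval.

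**What to change.** In Section 15.4:
- Change the stated maximum width from 0.404 to 0.456.
- Replace the table values for 1 to 11 responders with 0.260, 0.311, 0.350, 0.381, 0.406, 0.425, 0.439, 0.449, 0.454, 0.456 and 0.454.
- State that the prior is Beta(1,1) and the interval equal-tailed, so that the table can be reproduced and the final analysis follows the same convention.

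Relabelling the table as 95% would not do, because it would contradict the Bonferroni correction in the same paragraph.

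Optionally, since the table covers only N=20, add that a cohort closing at N=12 can have a wider 97.5% interval: up to 0.533 under the 50% rule (4 or 8 of 12) and up to 0.557 under the once-weekly 25% rule (6 of 12). Its absence is not an error.

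The cost is one number in one sentence, 11 table values and a clarifying phrase. The stated precision becomes less favourable by at most 0.052; design, sample size and analysis stay as they are.

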15. STATISTICAL CONSIDERATIONS

15.1 Study Design/Description

This is a Phase IIa open label dose-finding trial of low dose apalutamide in prostate cancer patients scheduled to undergo radical prostatectomy. The study is expected to include 2 dose groups. Up to 20 participants will be accrued into each dose group to initiate agent intervention.

The decision of dose de-escalation/escalation will be based on the PSA response. A participant with $\geq 25\%$ decline in serum PSA level is considered as a responder. For participants who do not complete the intervention and without post-intervention PSA value, we will conservatively assume the PSA decline to be $<25\%$, considered as a non-responder.

Accrued participants in the first dose cohort will receive apalutamide 60 mg MWF/wk for 4-8 weeks prior to radical prostatectomy. Based on the PSA response, an additional cohort of participants will receive a de-escalated dosing regimen at 60 mg once per week, or an escalated dosing regimen at 60 mg daily for 4-8 weeks prior to prostatectomy. To improve the efficiency of trial conduct, a continuous monitoring plan will be used for efficacy/futility evaluation after 12 participants have completed the dosing regimen. A PSA response rate of $\geq 50\%$ is considered sufficient for studying the 60 mg MWF/wk and the 60 mg daily dose in future active surveillance studies. The posterior probabilities of observing a response rate $\geq 50\%$ are summarized below based on the observed number of responders (N_r) and a non-informative prior for $N=12-20$ evaluable participants.

N_r	$N=12$	$N=13$	$N=14$	$N=15$	$N=16$	$N=17$	$N=18$	$N=19$	$N=20$
0	0.01	0.01	0.00	0.00	0.00	0.00	0.00	0.00	0.00
1	0.17	0.09	0.05	0.03	0.01	0.01	0.00	0.00	0.00
2	1.12	0.65	0.37	0.21	0.12	0.07	0.04	0.02	0.01
3	4.61	2.87	1.76	1.06	0.64	0.38	0.22	0.13	0.07
4	13.34	8.98	5.92	3.84	2.45	1.54	0.96	0.59	0.36
5	29.05	21.20	15.09	10.51	7.17	4.81	3.18	2.07	1.33
6	50.00	39.53	30.36	22.72	16.62	11.89	8.35	5.77	3.92
7	70.95	60.47	50.00	40.18	31.45	24.03	17.96	13.16	9.46
8	86.66	78.80	69.64	59.82	50.00	40.73	32.38	25.17	19.17
9	95.39	91.02	84.91	77.28	68.55	59.27	50.00	41.19	33.18
10	98.88	97.13	94.08	89.49	83.38	75.97	67.62	58.81	50.00
11	99.83	99.35	98.24	96.16	92.83	88.11	82.04	74.83	66.82
12	99.99	99.91	99.63	98.94	97.55	95.19	91.65	86.84	80.83
13	NA	99.99	99.95	99.79	99.36	98.46	96.82	94.23	90.54
14	NA	NA	100.00	99.97	99.88	99.62	99.04	97.93	96.08
15	NA	NA	NA	100.00	99.99	99.93	99.78	99.41	98.67

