15.9 Interim Analysis

As described above, a continuous monitoring plan will be used for efficacy/futility evaluation after 12 participants have completed the dosing regimen and the dose cohort will be stopped early for efficacy or futility. Accrual, data collection, and any adverse events will be monitored on a regular basis.

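### Section 15.4 states primary-endpoint precision only for 20 participants and at the wrong level, while the Section 15.1 rule usually closes a cohort at 12 to 18 evaluable men

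*Combined protocol and SAP*

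**What the plan says.** Section 15.4 sets the interval level by a correction for two cohorts: "we conservatively use Bonferroni correction while constructing the credible intervals for two dose groups". The interval comes from a posterior "derived from a non-informative prior for the response rate". Its precision statement is "A sample size of 20 participants produces a two-sided 97.5% CI for the response rate with a width no wider than 0.404", followed by a table of widths for 1 to 11 responders, all at N=20. Section 15.3 gives only a cap of 20 per dose group and accrual rates.

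Section 15.1 states that "a continuous monitoring plan will be used for efficacy/futility evaluation after 12 participants have completed the dosing regimen". A cohort closes when the posterior probability of meeting its target is at least 80% or at most 20%. Otherwise "the evaluation will be repeated with one additional evaluable participant, using the same criteria, up to a total of 20 evaluable participants". Section 15.9 repeats that "the dose cohort will be stopped early for efficacy or futility". The target is 50% for the Monday-Wednesday-Friday and daily regimens and 25% for the once-weekly regimen. No section gives an interval width for 12 to 19 participants or a distribution of the final cohort size.

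**The concern.** The N=20 width is the only precision the plan offers for its primary endpoint, but 20 is a cap that the monitoring rule often prevents a cohort from reaching. A reader who takes 0.404 as the precision of the design will expect a narrower interval than many cohorts can give.

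This matters because the response rates are meant to guide later work. Reaching the 50% target "is considered sufficient for studying the 60 mg MWF/wk and the 60 mg daily dose in future active surveillance studies", and reaching the 25% target "is considered sufficient for using this regimen as the starting regimen in future active surveillance studies". Planners of those studies need to know how well each rate will be estimated.

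**Working it through.** **Inputs.** Targets, 80%/20% limits, first look at 12 and cap of 20: Section 15.1. Interval level and stated widths: Section 15.4. The prior is not named. Beta(1,1) is inferred because it reproduces the Section 15.1 tables (for example 4/12 gives 13.34 against 50% and 79.40 against 25%).

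**Step 1: reproduce the stated figure.** Width = upper minus lower equal-tailed quantile of Beta(1+x, 1+n−x). For n=20 and x=1 to 11:
- 95%: 0.226, 0.273, 0.309, 0.337, 0.359, 0.376, 0.389, 0.397, 0.403, 0.404, 0.403. All eleven table rows match.
- 97.5%: 0.260, 0.311, 0.350, 0.381, 0.406, 0.425, 0.439, 0.449, 0.454, 0.456, 0.454. None matches.

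So the table holds 95% widths, and the 97.5% maximum at N=20 is 0.456. A 97.5% maximum of 0.404 or less would need N=27 (0.402).

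**Step 2: where the 50%-target rule can stop.** From the protocol's own table, 4/12 (13.34), 5/14 (15.09), 6/16 (16.62) and 7/18 (17.96) close for futility. Their mirror images 8/12 (86.66), 9/14 (84.91), 10/16 (83.38) and 11/18 (82.04) close for efficacy. At odd N, every count reachable from an open state stays between 20 and 80 (for example 5/13 = 21.20 and 8/13 = 78.80). Stops before 20 therefore occur only at 12, 14, 16 and 18.

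**Step 3: stopping probabilities at a true rate of 0.5** (weights out of 4096 = 2^12).
- Close at 12: 2 × (1+12+66+220+495) = 1588, or 38.8%. Open at 5, 6, 7 responders: 792, 924, 792.
- Close at 14: (792+792)/4 = 396. Open at 6, 7, 8: 627, 858, 627.
- Close at 16: (627+627)/4 = 313.5. Open at 7, 8, 9: 528, 742.5, 528.
- Close at 18: (528+528)/4 = 264.
- Total before 20: (1588+396+313.5+264)/4096 = 2561.5/4096 = 62.5%. This is the minimum over true rates.
- Mean N = (12×1588 + 14×396 + 16×313.5 + 18×264 + 20×1534.5)/4096 = 15.9. Mean N is 13.4 at 0.3 or 0.7 and 12.3 at 0.2 or 0.8.

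**Step 4: widths at closing outcomes.**

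| Rule | Outcome | 95% | 97.5% |
|---|---|---|---|
| 50% | 4/12 or 8/12 | 0.476 | 0.533 |
| 50% | 5/14 or 9/14 | 0.453 | 0.509 |
| 50% | 6/16 or 10/16 | 0.432 | 0.487 |
| 50% | 7/18 or 11/18 | 0.414 | 0.467 |
| 50% | 10/20 (widest at 20) | 0.404 | 0.456 |
| 25% | 6/12 | 0.497 | 0.557 |
| 25% | 5/13 | 0.472 | 0.530 |
| 25% | 5/14 | 0.453 | 0.509 |
| 25% | 5/15 | 0.435 | 0.489 |
| 25% | 6/17 | 0.417 | 0.470 |
| 25% | 6/18 | 0.403 | 0.454 |

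**Step 5: effect of early closing with the level held fixed.** Compare 95% widths with 0.404; the same outcomes exceed 0.456 at 97.5%. At a true rate of 0.5 under the 50% target, every early stop exceeds the N=20 maximum except 0, 1, 2, 10, 11 or 12 of 12. Those have weight 2×(1+12+66) = 158, so the probability is (2561.5−158)/4096 = 58.7%. The same recursion gives:

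| Rule | True rate | Closes before 20 | Width above N=20 maximum | Mean 95% width |
|---|---|---|---|---|
| 50% | 0.1 or 0.9 | – | 11% | 0.341 |
| 50% | 0.2 or 0.8 | 98.9% | 43% | 0.402 |
| 50% | 0.3 or 0.7 | 90.5% | 65.2% | 0.430 |
| 50% | 0.4 or 0.6 | 72.8% | 64.2% | 0.434 |
| 50% | 0.5 | 62.5% | 58.7% | 0.432 |
| 25% | 0.25 | 60.8% | 32.7% | 0.385 |
| 25% | 0.3 | 67.8% | 50.4% | 0.412 |
| 25% | 0.4 | 86.4% | 80.0% | 0.456 |

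The 25%-target rule has its lowest chance of closing before 20, 59.6%, at a true rate of 0.22.

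**The case against.** The strongest reply is that the sentence in Section 15.4 speaks only of 20 participants, and that Sections 15.1, 15.3 and 15.9 openly call 20 a cap. That stands. A reader might infer that early closing makes the sentence false, but the documents claim nothing about smaller cohorts. What makes the figure wrong is the interval level.

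Three other strong readings also fail.
- One might set the 97.5% mean widths of about 0.45–0.49 (50% target, true rates 0.2–0.8) against 0.404 and blame early closing for the whole gap. Much of it is the level error: on one level the means are 0.402–0.434 against 0.404, or 0.454–0.489 against 0.456.
- One might quote the largest width at each N (0.557 at 12, 0.526 at 14, 0.499 at 16, 0.476 at 18) for the 50% target. Those belong to 6/12, 7/14, 8/16 and 9/18, where the posterior is 50.00 and the cohort stays open.
- One might say most cohorts lose precision whatever the true rate. Step 5 shows that this depends on the rate and the rule.

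Overrun also counts. Section 15.6 analyses everyone with endpoint data, and no section pauses accrual during an evaluation. If 2, 4 or 6 further men are added (an assumption, capped at 20), the chance of an analysed N below 20 under the 50% target falls to 56%, 48% or 39% at a true rate of 0.5, and to 87%, 81% or 73% at 0.3 or 0.7. So near 0.5, with four or more extra men, most cohorts would be analysed at 20.

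Finally, no dose decision uses the width, and the reported interval will show its own width. That limits the consequence to planning and interpretation.

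**Conclusion.** The concern holds in a limited form. The plan's only precision figure describes a size that at least about 60% of cohorts will not have reached at the closing decision, whatever the true rate. It is also computed at 95% while labelled 97.5%. The widest 97.5% interval at closure is 0.533 under the 50% target and 0.557 under the 25% target, against 0.404 stated and 0.456 correct at N=20. Early closing by itself is a moderate effect at middling response rates and a small one at extreme rates.

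These results assume a Beta(1,1) prior, equal-tailed intervals, independent responses, a look after every evaluable man from the 12th, and no overrun. The correction is worth making, but the escalation and closing rules are unaffected.

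**What to change.** Replace the precision sentence and the width table in Section 15.4 with the following:
- 97.5% widths, recomputed at that level, for the outcomes at which each rule can actually stop. For the 50% target these are N=12, 14, 16, 18 and 20. For the 25% target they are N=12, 13, 14, 15, 17, 18 and 20. Step 4 gives the main entries.
- The distribution of stopping size and the expected width, over a stated range of true response rates, for each rule.
- The name of the prior.
- A note that these are sizes at the closing decision, and that men still on treatment may raise the analysed number.

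Do not list per-N maxima that cannot occur at closure. Adding rows for smaller N without recomputing the level would leave the N=20 figure wrong, and correcting the level alone would leave the sizes unrepresentative.

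The cost is one restated sentence and table, with a less favourable stated precision. Sample size, monitoring and conduct do not change.
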